#### *Secondary Objective*

1. To determine if the change in surface temperature over the course of treatment for cellulitis is predictive of clinical response to therapy. A demonstrated association would allow clinicians to objectively assess treatment progress at the bedside as well as provide a good surrogate outcome in clinical trials. We hypothesize that the temperature

differential will decrease over the course of treatment and predict clinical improvement.

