This data will be collected and managed using either the REDCap electronic data capture tools hosted at the McGill University Health Centre or another secure database system requiring password protected individually identified user accounts to access it [11]. Data will initially be stored by MRN (without name) but after all follow up visits are complete will be coded to ensure patient confidentiality (one-way hash of the MRN). The infectious diseases clinicians will be blinded to the result of the surface temperature measurement.

We will then compare the temperature difference between the affected and non-affected limbs with the current gold standard: the clinical diagnosis of the attending infectious diseases physician. This will yield estimates of sensitivity and specificity of the diagnostic test using expert clinical judgement as the gold standard.

In patients with cellulitis who are admitted for intravenous antibiotic therapy, we will perform daily measurements as described above throughout their admission. We will continue to record clinical data and laboratory data as above throughout admission for these patients. We will ultimately use statistical methods to characterize the relationship between skin surface temperature, expert clinical diagnosis of cellulitis and response to therapy (length of stay, duration of therapy, need for escalation in therapy, etc).

The study will be conducted until enrolment is completed. The anticipated study dates are September 1st 2018 to January 1st 2019.

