### *Statistical Analysis:*

For our primary aim, classical 2 x 2 tables will be used to evaluate the sensitivity and specificity of skin surface temperature in predicting cellulitis, as diagnosed by the attending infectious diseases specialist. A temperature difference of 0.5°C between the area of suspected cellulitis and an average of non-affected areas will be considered significant in the first attempt.

With regards to our secondary aim, we will use multivariate analysis and logistic regression to determine relationships between change in temperature differential and clinical response. Response to therapy will be defined on the basis of clinical and laboratory data and will consider the following information:

- Days of fever (i.e the number of calendar days since enrolment in which a temperature of 38.0 or higher was recorded)
- Days of intravenous antimicrobial therapy for cellulitis
- Days of hospitalization for cellulitis (including days in the ER)
- Total number of days of antibiotics given for cellulitis
- Days to normalization of white blood cell count
- Days to normalization of C-Reactive Protein
- Patient reported outcomes:
  - Patient global impression of improvement scale
    - Select the option which best describes your cellulitis now, as compared to how it was when you arrived in the emergency department:
    - Very much better (1)
    - Much better (2)
    - A little better (3)
    - No change (4)
    - A little worse (5)
    - Much worse (6)
    - Very much worse (7)

*Study Funding and Compensation*

This study is not externally funded. The fees for purchasing the infrared thermometer will be borne by the investigators. Physicians and patients will not receive compensation for their participation in this pragmatic study.

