Our goal was to detect a 12% difference in skin surface temperature between limbs with a statistical power of 80%. Assuming an alpha value of 5%, we estimated that we would need to enroll a minimum of 31 patients. To more confidently establish sensitivity and specificity estimates and to be more certain of an adequate sample size, we sought to enrol 50 patients.

With the “*cutpt*” command in STATA v. 16 (Statacorp LP, USA), we will use Youden’s method² to determine the temperature difference which best differentiated cellulitis from pseudocellulitis. We will then use bootstrapping (500 repetitions) to estimate 95% confidence intervals for the sensitivity, specificity and the area under the receiver operating curve (c-statistic). Then, using the point estimates for sensitivity and specificity we will construct a plot of pre-test vs. post-test probability as a function of test result. We will also calculate the temperature difference which gave the maximal specificity and include it for reference.

Analysis of Improvement of Cellulitis:

For those who were admitted to hospital and who agreed to be followed we will calculate the FDA criteria for early response (percent reduction in the lesion size at 48 to 72 hours compared to baseline) wherein clinical response in a patient generally is defined as a percent reduction in lesion size greater than or equal to 20 percent compared to baseline. With the “*cutpt*” command in STATA v. 16 (Statacorp LP, USA), we will use Youden’s method² to determine the temperature difference which best matches early response. We will then use bootstrapping (500 repetitions) to estimate 95% confidence intervals for the sensitivity, specificity and the area under the receiver operating curve (c-

statistic). We will also calculate the temperature differences which give the maximal sensitivity and specificity and include it for reference.

We will also explore the relationship between change in lesion size and temperature difference between limbs graphically and calculate an estimate of the correlation using the most appropriate regression method based on inspection.

REFERENCES

2. Youden WJ. Index for rating diagnostic tests. *Cancer.* 1950;3(1):32–35.

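### The secondary analysis does not define its temperature marker or say whether the enrolment differential enters the model, so cooling and starting severity may be mixed

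*Protocol*

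**What the plan says.** The Protocol's Secondary Objective is "To determine if the change in surface temperature over the course of treatment for cellulitis is predictive of clinical response to therapy". Its stated uses are to "objectively assess treatment progress at the bedside as well as provide a good surrogate outcome in clinical trials". For the analysis, the Protocol's Statistical Analysis section says "we will use multivariate analysis and logistic regression to determine relationships between change in temperature differential and clinical response". It lists no covariates. On the outcome it says "Response to therapy will be defined on the basis of clinical and laboratory data and will consider the following information", followed by durations (fever, intravenous therapy, hospital stay, total antibiotics, days to normal white cell count and C-reactive protein) and a patient-reported scale.

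The SAP, under Analysis of Improvement of Cellulitis, takes one binary outcome at 48 to 72 hours: "percent reduction in lesion size greater than or equal to 20 percent compared to baseline". It uses Youden's method "to determine the temperature difference which best matches early response", with bootstrap intervals for sensitivity, specificity and the c-statistic. It also plans to relate lesion-size change to the temperature difference between limbs and "calculate an estimate of the correlation using the most appropriate regression method based on inspection". No covariate is named in either analysis.

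The enrolment differential is available. Both limbs are measured at recruitment, and for admitted patients with cellulitis the Protocol's Study Protocol section adds "we will perform daily measurements as described above throughout their admission".

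**The concern.** Two gaps combine.

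First, the marker is not fixed. The Protocol names a change. The SAP's wording fits either a change from enrolment or the between-limb level at a given time. The two relate to the starting differential with opposite signs: a hotter starting limb tends to show a larger fall, but also a higher later level.

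Second, neither document says whether the enrolment differential is in the model. If a hotter limb at enrolment marks a more severe case, a large fall partly flags severity. An unadjusted slope or ROC area then cannot separate two statements: that cooling predicts response, and that starting severity predicts response.

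This matters most for the surrogate claim in the Secondary Objective and the Innovation section. That claim needs evidence that temperature during treatment adds to what was known at enrolment.

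**Working it through.** **Plan's own figure.** The documents give no sample size, effect or variance for the secondary analysis, so there is nothing to reproduce. The stated minimum of 31 and target of 50 belong to the between-limb and diagnostic aim. Everything below rests on assumed inputs.

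**Notation.** B is the enrolment differential, F the follow-up differential, and D = B − F the fall. r = corr(B, F) and k = SD(F)/SD(B).

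**Step 1: is a fall tied to its baseline?** corr(B, D) = (1 − rk)/√(1 + k² − 2rk). With k = 1 this is √((1 − r)/2):
- r = 0.3: √0.35 = 0.59
- r = 0.5: √0.25 = 0.50

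Over k = 0.4 to 1.0 and r = 0 to 0.7 it runs from 0.39 to 0.93. It is positive throughout.

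**Step 2: false association when cooling carries no information.** Assume 35 followed inpatients, k = 1, and a log duration outcome Y (higher is worse) that depends on B only, with corr(B, Y) = g. Then corr(D, Y) = g × corr(B, D). The two-sided 5% rejection rate follows approximately from Fisher's z = atanh(corr) × √(35 − 3):

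| r | g | corr(D, Y) | z | Rejection rate |
|---|---|---|---|---|
| 0.5 | 0.3 | 0.150 | 0.86 | 14% |
| 0.3 | 0.3 | 0.177 | 1.02 | 17% |
| 0.5 | 0.5 | 0.250 | 1.45 | 30% |
| 0.3 | 0.5 | 0.296 | 1.73 | 41% |

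Repeated simulation of the linear model gives about 12 to 42% over these cells. Almost all rejections are in the wrong direction (larger fall, longer course). With B in the model the rate is about 5%.

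**Step 3: the same case if the marker is the level F.** Now corr(F, Y) = r × g, which runs from 0.3 × 0.3 = 0.09 to 0.5 × 0.5 = 0.25. By the same formula the rejection rate is about 8 to 30%, and mostly in the hypothesised direction (cooler limb, shorter course). So the undefined marker decides which way the distortion goes.

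**Step 4: a logistic version with a real cooling effect.** Let logit(response) = βD − γB, with β = 1 per SD of B. To a first approximation the unadjusted slope is β − γ(1 − rk)/(1 + k² − 2rk). For r = 0.5 the last factor is 0.75/0.75 = 1.0 at k = 0.5, and 0.5/1 = 0.5 at k = 1. Simulated large-sample values, where the adjusted log odds ratio is 1.0 in every row:

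| k | γ | Unadjusted log OR | AUC of the fall |
|---|---|---|---|
| 0.5 | −1 | 1.90 | 0.83 |
| 0.5 | 0 | 1.00 | 0.71 |
| 0.5 | 0.5 | 0.49 | 0.62 |
| 0.5 | 1 | 0.00 | 0.50 |
| 0.5 | 2 | −0.83 | 0.32 |
| 1 | −1 | 1.32 | 0.79 |
| 1 | 0 | 1.00 | 0.74 |
| 1 | 1 | 0.43 | 0.62 |
| 1 | 2 | 0.00 | 0.50 |

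Over the wider grid of k and r, the unadjusted link vanishes when γ/β is between 0.83 and 2.0. It reverses above that, and is inflated when γ is negative.

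**Step 5: the price of adjusting.** If γ = 0 and the effect acts through the raw fall, adjustment costs power because B and D are collinear. In the linear model with 35 patients and an effect of 0.3 SD, power goes from about 41–44% to 28–34%. In the logistic model with 50 patients, k = 0.5 and r = 0.5, it goes from 77% to 25%.

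**The case against.** The strongest reply has four parts.

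1. **The Protocol does not plan an unadjusted analysis.** A reader might infer that it rules out baseline adjustment. It does not: it promises a multivariate analysis with an unlisted covariate set. The fault there is under-specification. In the SAP, by contrast, a single-marker analysis is what is written.

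2. **The SAP's predictor may not be a change score.** A reader might carry the hotter-limb, larger-fall argument straight over to the SAP. The wording does not support that, because the marker may be a level. This stands, and it is why defining the marker comes first. It does not remove the problem, since a later level also correlates with baseline (Step 3).

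3. **The severity link is assumed.** The documents contain no data on whether a hotter limb responds worse, and the SAP's outcome is a percentage of baseline lesion size, for which such a link is less obvious than for hospital days. With γ = 0 there is no bias. This stands.

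4. **The unadjusted association is a legitimate quantity.** For a simple bedside rule, the crude ROC answers a fair question. This also stands, and is a reason to keep it. It does not meet the surrogate aim.

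**Conclusion.** The point holds as a gap in specification with a plausible consequence. The Protocol names no covariates for a change-score predictor. The SAP's analysis is unadjusted as written and leaves the marker undefined. If the enrolment differential tracks severity, the planned association mixes cooling with severity.

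The 12 to 42% rejection rate (about 5% adjusted) rests on 35 patients, equal SDs, r of 0.3 to 0.5, a baseline-outcome correlation of 0.3 to 0.5, no cooling effect and a linear model of a log duration. It illustrates the Protocol's duration outcomes and is not an estimate for the SAP's early-response ROC. Step 4 is closer to that analysis, but its inputs are also assumed.

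Two stronger conclusions are tempting and not supported. One is that the plan will hide or reverse a real effect: the direction depends on a link that the documents do not report, and the opposite sign inflates the association. The other is that adjusting improves power in any case: when baseline has no independent link and the effect lies in the raw fall, it lowers power. The change should be made, with moderate confidence in its importance.

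**What to change.** In the Protocol's Statistical Analysis section and the SAP's Analysis of Improvement of Cellulitis:

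- State whether the marker is the fall since enrolment or the between-limb level, and at what time point.
- Keep the planned unadjusted Youden and ROC analysis.
- Beside it, add a logistic model of early response on the 48 to 72 hour differential and the enrolment differential. This equals a model of fall plus baseline: with F = B − D, b₁F + b₂B = −b₁D + (b₁ + b₂)B.
- Report the adjusted odds ratio with its interval, and the gain in c-statistic over the enrolment differential alone.
- Name any other covariate in advance, and keep the number small. The target is 50 patients, and only those admitted and followed contribute.

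The cost is SAP wording, one covariate already collected and one degree of freedom. The downside is lower power if baseline has no independent link with response, which is why both analyses should be reported.

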Handheld Infrared Thermometer to Evaluate Cellulitis (HI-TEC)

Statistical Analysis Plan Version 1.0 1st of March 2020

Study ID: 2019-4850

NCT03846635

Participants

Eligible patients were at least 18 years of age and had suspected cellulitis restricted to an arm or leg (without involvement of the trunk, genitalia or head and neck). Consultation of an infectious disease specialist was required for enrolment. Patients were excluded if they had received empiric therapy for cellulitis for greater than 24 hours before recruitment or if they had a severe skin infection that would ultimately need operative management (such as deep abscess or necrotizing fasciitis). Patients who were unable to give informed consent, as well as patients with amputated contralateral limbs or known severe dysautonomia causing limb temperature dysregulation were also excluded.

Diagnostic Procedure

At the time of recruitment, demographic data and key clinical information including medical history and laboratory results were collected. We used a MasterCraft Digital Temperature Reader infrared thermometer (Mastercraft Canada, Toronto, Canada) to measure skin surface temperature. This thermometer was chosen because it was previously validated against a medical-grade skin temperature device (Exergen DermaTemp)¹, is inexpensive (purchased for \$30.50 CAD), and is widely commercially available in Canada.

We performed duplicate measurements of the affected area, followed by measurements of the contralateral limb as close to the same location as possible. Before obtaining the measurement, patients were instructed to uncover the area for several minutes in order to avoid temperature fluctuation caused by clothing. Measurements were taken from a vertical distance of approximately 5-10 cm above the affected area. We then evaluated whether a difference in the average temperature between limbs was associated with a clinical diagnosis of cellulitis as determined by the blinded faculty infectious disease consultant. The treating team and the infectious disease specialist

remained blinded to the temperature measurements so that clinical decisions were not influenced by the results.

Analysis of Diagnosis of Cellulitis:

Our goal was to detect a 12% difference in skin surface temperature between limbs with a statistical power of 80%. Assuming an alpha value of 5%, we estimated that we would need to enroll a minimum of 31 patients. To more confidently establish sensitivity and specificity estimates and to be more certain of an adequate sample size, we sought to enrol 50 patients.

With the “*cutpt*” command in STATA v. 16 (Statacorp LP, USA), we will use Youden’s method² to determine the temperature difference which best differentiated cellulitis from pseudocellulitis. We will then use bootstrapping (500 repetitions) to estimate 95% confidence intervals for the sensitivity, specificity and the area under the receiver operating curve (c-statistic). Then, using the point estimates for sensitivity and specificity we will construct a plot of pre-test vs. post-test probability as a function of test result. We will also calculate the temperature difference which gave the maximal specificity and include it for reference.

Analysis of Improvement of Cellulitis:

For those who were admitted to hospital and who agreed to be followed we will calculate the FDA criteria for early response (percent reduction in the lesion size at 48 to 72 hours compared to baseline) wherein clinical response in a patient generally is defined as a percent reduction in lesion size greater than or equal to 20 percent compared to baseline. With the “*cutpt*” command in STATA v. 16 (Statacorp LP, USA), we will use Youden’s method² to determine the temperature difference which best matches early response. We will then use bootstrapping (500 repetitions) to estimate 95% confidence intervals for the sensitivity, specificity and the area under the receiver operating curve (c-

statistic). We will also calculate the temperature differences which give the maximal sensitivity and specificity and include it for reference.

We will also explore the relationship between change in lesion size and temperature difference between limbs graphically and calculate an estimate of the correlation using the most appropriate regression method based on inspection.

REFERENCES

2. Youden WJ. Index for rating diagnostic tests. *Cancer.* 1950;3(1):32–35.

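### The Youden cut-off is chosen and its sensitivity and specificity are estimated in the same patients without correction, so both are overstated on average and the post-test plot looks too informative

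*SAP*

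**What the plan says.** In the SAP's Analysis of Diagnosis of Cellulitis, Stata's cutpt command is used with Youden's method to "determine the temperature difference which best differentiated cellulitis from pseudocellulitis". The next step is to "use bootstrapping (500 repetitions) to estimate 95% confidence intervals for the sensitivity, specificity and the area under the receiver operating curve". Then, "using the point estimates for sensitivity and specificity we will construct a plot of pre-test vs. post-test probability as a function of test result". A second cut-off is added: "We will also calculate the temperature difference which gave the maximal specificity and include it for reference".

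The Analysis of Improvement of Cellulitis repeats the method in admitted patients who agreed to follow-up, to "determine the temperature difference which best matches early response". It adds two extreme cut-offs: "We will also calculate the temperature differences which give the maximal sensitivity and specificity and include it for reference".

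On size, the SAP states "we sought to enrol 50 patients". The Protocol's Sample Size section aims for 50 with a cellulitis diagnosis. Neither gives the number without cellulitis.

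For the primary aim, the Protocol's Statistical Analysis section says "classical 2 x 2 tables will be used to evaluate the sensitivity and specificity of skin surface temperature in predicting cellulitis", at a provisional threshold of 0.5°C between the suspected area and an average of non-affected areas. The SAP does not carry this threshold forward. Its Diagnostic Procedure section uses the contralateral limb as comparator. Neither document mentions a split sample, cross-validation, external validation or optimism correction.

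**The concern.** A cut-off picked because it gives the best sum of sensitivity and specificity in a sample owes part of that result to chance in that sample. In new patients the sum will on average be lower. A bootstrap used only for intervals leaves the point estimates unchanged, and the plot is built from the point estimates.

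Sensitivity and specificity are the stated output of the diagnostic comparison in the Protocol's Study Protocol and Statistical Analysis sections. The Primary Objective looks towards a tool for clinicians without infectious-disease expertise, and these are the likely readers of a post-test plot. Overstated accuracy would make a positive result look more conclusive, and a negative result more reassuring, than the cut-off will be in practice.

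**Working it through.** **No plan figure to reproduce.** The documents state no sensitivity, specificity or bias. The minimum of 31 patients cannot be checked without a standard deviation, and this point does not depend on it.

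**Inputs.** From the documents: Youden selection in the study data; 50 patients in total (SAP) or 50 with cellulitis (Protocol); 500 resamples for intervals. Assumed: binormal data, AUC 0.70 to 0.90, and the case mixes shown. The simulation is rank-based, so it holds for any monotone transform of binormal data.

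**Direction.** Let J(c) = Se(c) + Sp(c) − 1 be the true index at cut-off c, Ĵ(c) its sample estimate, c\* the cut-off maximising Ĵ, and c0 the cut-off maximising J. At the fixed c0, Ĵ is unbiased. Since Ĵ(c\*) ≥ Ĵ(c0),

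E[Ĵ(c\*)] ≥ E[Ĵ(c0)] = J(c0) ≥ E[J(c\*)].

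So the index is overstated on average whatever the distribution. That each component is overstated on average was found by simulation, in every setting run.

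**Size.** Mean inflation of the index, 40,000 trials per cell:

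| Cellulitis/other | AUC 0.70 | 0.80 | 0.90 |
|---|---|---|---|
| 40/10 | 0.175 | 0.155 | 0.130 |
| 35/15 | 0.150 | 0.133 | 0.110 |
| 25/25 | 0.134 | 0.118 | 0.097 |
| 50/10 | 0.172 | 0.152 | 0.129 |
| 50/20 | 0.128 | 0.112 | 0.093 |
| 50/50 | 0.093 | 0.080 | 0.066 |

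At 40/10 and AUC 0.80, apparent sensitivity/specificity averages 77%/80% against 72%/69% true: (77 + 80) − (72 + 69) = 16 points. The smaller class carries more of the bias. The index exceeds the truth in 84–93% of trials, and both components do so together in 54–65%.

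**Plot, 50% pre-test.** After a positive result, P = Se/(Se + 1 − Sp). After a negative result, P = (1 − Se)/((1 − Se) + Sp). At 40/10:

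- Positive: 0.77/(0.77 + 0.20) = 79% apparent; 0.72/(0.72 + 0.31) = 70% true.
- Negative: 0.23/(0.23 + 0.80) = 22% apparent (23% before the inputs are rounded); 0.28/(0.28 + 0.69) = 29% true.

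The same calculation gives 75%/22% against 70%/28% at 25/25, and about 75%/24% against 71%/28% at 50/50.

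**Intervals.** Coverage of true specificity at the reported cut-off by nominal 95% intervals (AUC 0.80, 1,000 trials of 500 resamples):

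| Cellulitis/other | Re-selected, percentile | Re-selected, normal-based | Fixed cut-off, percentile |
|---|---|---|---|
| 40/10 | 0.75 | 0.78 | 0.74 |
| 35/15 | 0.85 | 0.87 | 0.82 |
| 25/25 | 0.90 | 0.94 | 0.89 |
| 50/10 | 0.72 | 0.77 | 0.74 |
| 50/20 | 0.87 | 0.90 | 0.83 |
| 50/50 | 0.92 | 0.97 | 0.89 |

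The SAP says neither whether the cut-off is re-selected nor which interval type is used.

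**Extreme cut-offs.** A cut-off above the highest non-case has 100% specificity in the sample by construction. With m non-cases, the one-sided exact 95% lower limit is 0.05^(1/m): 55% for m = 5, 74% for 10, 89% for 25 and 94% for 50.

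**Early response.** The documents give no number. With an assumed 20 to 30 patients (10/10, 15/5, 15/15, 20/10), the index is inflated by 0.13 to 0.25.

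**Can it be corrected?** Stratified cross-validation with the cut-off re-selected in each training set, and k = 10 or the smaller class size if below 10, removed 92–111% of the index bias. At AUC 0.80, cross-validated against true sensitivity/specificity was:

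- 72.7/68.6 against 72.7/68.4 at 40/10
- 71.6/69.4 against 72.6/69.3 at 25/25
- 72.4/70.4 against 72.5/70.1 at 50/50
- 70.1/69.4 against 71.8/68.5 at 15/5

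Two alternatives did worse. Leave-one-out left 17–38% of the bias when the classes were equal in size. A bootstrap optimism correction at 35/15 with 1 SD separation (250 trials) moved the index from 73.5 + 76.1 − 100 = 49.6 points to 70.8 + 69.9 − 100 = 40.7, against a true 69.2 + 65.5 − 100 = 34.7. It removed 8.9 of 14.9 points, about 60%.

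**The case against.** The primary objective is association. The AUC addresses that, and it does not depend on a chosen cut-off. The SAP openly describes deriving a cut-off, claims no validation, and gives the extreme cut-offs only for reference. The Protocol's fixed 0.5°C table carries no selection bias, and the SAP does not expressly withdraw it. All magnitudes rest on an assumed AUC and case mix.

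These points limit the weight of the concern but do not remove it. The SAP does not label the cut-off or the plot exploratory, and it does not use the 0.5°C rule. The direction for the index needs no assumption about AUC or case mix.

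Four technical points stand:

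- The post-test figures insert mean sensitivity and specificity into the formula. Averaging trial-level post-test probabilities at 40/10 gives 83%/22% against 72%/27%: same direction, different size.
- With normal-based intervals and re-selection, coverage of specificity is adequate at 25/25 and 50/50. The under-coverage belongs mainly to small non-cellulitis groups.
- Correction removes average bias but hardly improves a single trial's plot. Root-mean-square error after a positive result went from 0.140 to 0.124 at 40/10, 0.081 to 0.085 at 25/25 and 0.059 to 0.061 at 50/50. After a negative result it went from 0.074 to 0.085, 0.091 to 0.081 and 0.061 to 0.057.
- If cut-offs are restricted to observed values and the highest reading is a non-case, maximal specificity falls short of 100%. This occurred in about 1–5% of simulated trials.

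**Conclusion.** The concern holds and should be fixed. As planned, sensitivity and specificity at the Youden cut-off are on average better than the cut-off would achieve in new patients, and the plot is too high after a positive result and too low after a negative one. Over AUC 0.70–0.90, the index is inflated by 0.10–0.18 with 50 patients in total and by 0.07–0.17 with 50 cases plus 10–50 others. The actual size in this trial is unknown, because the documents give neither AUC nor case mix. This is a statement about averages: a given sample can fall either way. The bias is measured against true performance at the chosen cut-off, which is what a reader of the plot would rely on. The association objective is not compromised.

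**What to change.** Change the SAP as follows:

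1. Label the Youden cut-off as derived in this sample. Beside the apparent values, report sensitivity and specificity from stratified k-fold cross-validation that re-runs cutpt in every training set, repeated 50 times with a fixed seed. Take k = 10, or the size of the smaller class if below 10; that class must have at least 2 patients. Use the same rule for early response (for example k = 5 at 15/5). Do not substitute leave-one-out.
2. State that the bootstrap re-selects the cut-off in each resample, name the interval type, and say that the intervals describe the apparent estimates and may under-cover. State also that cross-validation removes average bias but does not make one trial's specificity more precise.
3. Draw the plot, for positive and negative results, from the cross-validated values, named in advance as its source.
4. As a sensitivity analysis, give the 2x2 table with exact 95% intervals at 0.5°C, applied to the contralateral difference. Note that the Protocol set this value provisionally and for a different comparator.
5. Beside each maximal-specificity or maximal-sensitivity cut-off that classifies all m patients of the relevant class correctly, give the lower limit 0.05^(1/m).

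The cost is SAP wording and a short loop around cutpt, with no new data. Accuracy figures become less favourable. At AUC 0.80, root-mean-square error of specificity rises from 0.164 to 0.177 at 40/10, 0.097 to 0.111 at 25/25 and 0.068 to 0.081 at 50/50. That of sensitivity rises from 0.078 to 0.087 at 40/10. That of the index falls from 0.197 to 0.179, 0.157 to 0.139 and 0.109 to 0.099. Exact intervals at 0.5°C will be wide: 8/10 gives 44–97%, 20/25 gives 59–93% and 40/50 gives 66–90%. The cross-validated values and the plot come without intervals of their own, and the report should say so.

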### *Sample Size*

In order to detect a 12% difference in skin surface temperature between limbs with a statistical power of 80%, assuming an alpha value of 5%, we anticipate that we will need to enrol 31 patients at a minimum. To be certain that we will establish reasonable sensitivity and specificity estimates and that our sample size will be sufficient, we will aim to enrol 50 patients with a diagnosis of cellulitis.

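### The SAP's post-test probability curves are drawn from same-data point estimates, so they show no uncertainty and tend to be too favourable; a corrected, banded figure is a cheap improvement

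*SAP*

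**What the plan says.** In the SAP, under Analysis of Diagnosis of Cellulitis, three steps follow one another:

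- Youden's method is used to "determine the temperature difference which best differentiated cellulitis from pseudocellulitis". The SAP fixes no cut-off in advance.
- The uncertainty step is "bootstrapping (500 repetitions) to estimate 95% confidence intervals for the sensitivity, specificity and the area under the receiver operating curve". The SAP does not say whether the cut-off is chosen again in each repetition.
- Then, "using the point estimates for sensitivity and specificity we will construct a plot of pre-test vs. post-test probability as a function of test result".

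Neither document plans an interval for a likelihood ratio or a post-test probability, a band on the plot, or a correction for choosing the cut-off on the data used to assess it. The protocol's Statistical Analysis section plans only 2 x 2 tables for the primary aim.

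On numbers, the SAP says "we sought to enrol 50 patients", while the protocol's Sample Size section says "we will aim to enrol 50 patients with a diagnosis of cellulitis". Neither gives the number of patients without cellulitis, or an expected sensitivity or specificity.

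**The concern.** Post-test probability is a nonlinear function of sensitivity and specificity together. A reader with two separate confidence intervals cannot read off its interval, least of all when both estimates come from one data-chosen cut-off. A line drawn through the point estimates alone looks more exact than the study can make it.

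The line is also likely to be in the wrong place. Youden's method picks the cut-off at which sensitivity plus specificity happens to be highest in this sample, so both apparent values tend to be too high. The positive-test curve is sensitive to this because it depends on 1 minus specificity, a small quantity that may rest on a handful of false positives.

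At stake is how the diagnostic result is read: a positive test would seem to raise the probability of cellulitis more, and more surely, than the data support.

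**Working it through.** **The plan's own figure.** The only sample-size calculation ends in "we would need to enroll a minimum of 31 patients", for a 12% difference between limbs. It gives no standard deviation, so it cannot be reproduced. On the paired normal formula (two-sided) it would imply an SD of about 23.8%. It does not enter the plot and has no bearing on this point.

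**Inputs.** From the SAP: 50 patients, point-estimate curves, Youden cut-off on the same data. From the protocol: 50 patients with cellulitis. Assumed, because the documents are silent: the split, the accuracy and a 50% pre-test probability.

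**Step 1: width at a fixed cut-off.** Let TP, FN, FP and TN be the cell counts, with n1 cellulitis and n0 other patients.

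- LR+ = sens/(1 - spec); LR- = (1 - sens)/spec
- SE(log LR+) = sqrt(1/TP - 1/n1 + 1/FP - 1/n0); for LR-, use FN and TN in place of TP and FP
- 95% limits = LR x exp(±1.96 SE)
- post-test odds = pre-test odds x LR; at 50% pre-test, probability = LR/(1 + LR)

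Worked case, 35/15 with 28/35 and 12/15 correct: LR+ = 0.80/0.20 = 4.0. SE = sqrt(1/28 - 1/35 + 1/3 - 1/15) = sqrt(0.2738) = 0.523. Limits: 4.0 x exp(±1.026) = 1.43 to 11.16. Probability: 1.43/2.43 = 59% to 11.16/12.16 = 92%.

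All at sensitivity = specificity = 0.80:

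| Cellulitis / other | LR+ (95% limits) | After positive test | After negative test |
|---|---|---|---|
| 25/25 | 4.0 (1.78-8.97) | 80% (64-90%) | 20% (10-36%) |
| 30/20 | 4.0 (1.64-9.79) | 80% (62-91%) | 20% (11-35%) |
| 35/15 | 4.0 (1.43-11.16) | 80% (59-92%) | 20% (11-34%) |
| 40/10 | 4.0 (1.15-13.95) | 80% (53-93%) | 20% (11-33%) |
| 50/50 | 4.0 (2.26-7.08) | 80% (69-88%) | 20% (12-31%) |

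The last row is one reading of the protocol's target. Its number of others is assumed.

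**Step 2: other accuracies at 50 patients.** At 0.7/0.7, LR+ is 2.57 (1.31-5.05) with 25/25 and 2.33 (0.89-6.14) with 40/10. At 0.9/0.9 it is 7.33 (2.51-21.41) and 9.00 (1.40-57.95). Over 20 combinations of split and accuracy, the lower limit of LR+ lay between 0.89 and 2.51.

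**Step 3: optimism from the Youden cut-off.** Simulation of 4000 runs per split, binormal model, true optimum 0.80/0.80:

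| Split | Mean apparent J | Mean true J at chosen cut | Median apparent LR+ | Median true LR+ | Runs with apparent specificity 1 |
|---|---|---|---|---|---|
| 25/25 | 0.675 | 0.573 | 4.8 | 3.84 | 3% |
| 35/15 | 0.687 | 0.572 | 6.43 | 3.97 | 15% |
| 40/10 | 0.698 | 0.566 | 7.75 | 3.77 | 25% |

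At 50% pre-test, the apparent LR+ gives 4.8/5.8 = 83%, 6.43/7.43 = 87% and 7.75/8.75 = 89%. The true LR+ gives 3.84/4.84 = 79%, 3.97/4.97 = 80% and 3.77/4.77 = 79%; other runs put the true value as high as 81%. Where apparent specificity is exactly 1, the positive-test curve is 100% at every non-zero pre-test probability.

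**Step 4: which band works.** Under the same model, raw percentile limits with the cut-off re-selected in each draw ran from about 71-75% up to 100% for a positive test. They contained the true value in 87% (25/25), 86% (30/20), 78% (35/15) and 65% (40/10) of datasets. Another set of runs gave 83%, 82%, 77% and 60%. Log-likelihood-ratio intervals around optimism-corrected values covered about 96-98%.

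**The case against.** The strongest reply is that the uncertainty is not lost. The sentence before the plot plans 95% intervals for sensitivity and specificity, and the plot is a transform of those two quantities. No test or decision rule depends on it. That stands, and it keeps the severity modest. It does not give a reader the interval for post-test probability, and it does not address where the curve lies.

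Four stronger readings are tempting, and the documents do not support them:

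- *The plot is what a non-expert clinician will use.* The protocol's Primary Objective describes the temperature difference as a possible aid for such clinicians. Neither document names an audience for the plot.
- *The figure is a single firm curve.* It is a function of test result, so there is one curve for a positive and one for a negative test.
- *The data will allow anything from weak to strong evidence.* That depends on assumed accuracy and split. At 0.7/0.7 the upper end is only moderate, and with 50/50 at 0.8/0.8 the limits are 69-88%.
- *Specificity is the least precise quantity.* That requires patients without cellulitis to be the smaller group, which neither document states.

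It may also be said that a band around a biased line cures nothing, and that simply taking percentiles of the bootstrap draws would mislead. Both are correct, as Step 4 shows, and they determine the form of the fix.

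**Conclusion.** The point holds as a cheap improvement of modest severity. As specified, the curves show no uncertainty and tend to overstate what a positive test means. At 50 patients the optimism is roughly 83-89% apparent against 79-81% true, under a binormal model with true accuracy 80%/80% and 50% pre-test probability.

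The imprecision, under the same accuracy but at a fixed cut-off, is 80% with limits from 64-90% (25/25) to 53-93% (40/10) after a positive test, and 20% with limits of about 10-36% after a negative test. These widths are illustrations under stated assumptions, not properties of the trial's data, and they leave out the uncertainty in the cut-off itself.

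**What to change.** Amend the plotting sentence in the SAP's diagnostic analysis to specify:

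1. **Optimism correction from the planned 500 repetitions.** In each draw, re-select the Youden cut-off, record sensitivity and specificity in the draw, then apply that cut-off to the original data. Subtract the mean difference (draw minus original) from the apparent sensitivity and specificity.
2. **Curves and bands.** Draw the positive-test and negative-test curves from the corrected values, each with a pointwise 95% band obtained by passing the log-likelihood-ratio limits around those values through the pre-test odds.
3. **Empty cells.** State a continuity correction for use when there are no false positives or no false negatives.
4. **What not to use.** Do not take the band from raw percentile limits of the re-selected draws; they under-cover and reach 100%.

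The cost is a little more code and a figure that looks less decisive. No additional patients or measurements are needed.
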